All the relevant data will be compiled on a master chart first and then statistical analysis of the results will be obtained by using Windows based computer software facilities with Statistical Packages for Social Sciences (SPSS-24) (SPSS Inc, Chicago IL USA). The data will be analysed using Chi-square test and 't' test. The results will be presented in tables, figures, diagrams. All reported P values are two sided and $P < 0.05$ will be considered statistically significant.

Title of the Protocol

Free Breathing versus Deep Inspiration Breath Hold Technique in Adjuvant Radiotherapy for Left Sided Breast Cancer: A Dosimetric Comparison of Target Volumes, Heart and Left Lung

Name of the student : [name]

Place of study : Department of Clinical Oncology, BSMMU

: Department of Radiation Oncology, Combined Military Hospital

: Department of Oncology, Delta Hospital Limited

: Lab Aid Cancer Hospital

Type of the study : Quasi-Experimental study

Name of the guide : [name]. [name]
Associate Professor
Department of Clinical Oncology
Bangabandhu Sheikh Mujib Medical University (BSMMU)

Table of Contents

Serial No.	Topic	Page No.
1	Title	-
2	Introduction	1
3	Rationale of the study	6
4	Research question	7
5	Objectives	8
6	Materials & Methods	9
	a) Study design	9
	b) Duration of study	9
	c) Centre of study	9
	d) Study Population	9
	e) Sampling technique	9
	f) Sample size	10
	g) Selection criteria of patients	11
	h) Research Instrument	11
	i) Grouping	12
	j) Study procedure	12
	k) Case collection	14
	l) Pre-treatment evaluation	14
	m) Intervention	15
	n) Variables	15
	o) Data collection	16
	p) Consort flow chart	17
	q) Operational definition	18
	r) Analysis of Data	20
	s) Data presentation	20
	t) Quality assurance	20
	u) Timetable of the study	21
7	Ethical Considerations	22
8	Dummy tables	23
9	Limitations of the study	24
10	Reference	25
11	Budget	32
12	Appendices	Xiv

Introduction

“Cancer is a large group of diseases that can start in almost any organ or tissue of the body when abnormal cells grow uncontrollably, go beyond their usual boundaries to invade adjoining parts of the body and/or spread to other organs” (World Health Organization [WHO]). The incidence, prevalence and fatality of cancer is rising worldwide with the increase in life expectancy and change in lifestyle. It represents a significant global health, social and economic burden.

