[name].
3. Department of Oncology
Delta Hospital Limited
[name].
4. Lab Aid Cancer Hospital
[name].

Study Population

Carcinoma left breast patients attending the outpatient departments (OPD) of study centres for post mastectomy radiotherapy.

Sampling Technique

After meeting inclusion and exclusion criteria, participants will be enrolled in this study and then divided equally into 2 arms by purposive sampling.

Sample Size

For determination of sample size following formula has been applied:

$$n = \frac{2 \times \sigma^2 \times (Z_\alpha + Z_\beta)^2}{(\mu_1 - \mu_2)^2}$$

n = Sample size

μ_1 = Mean of control group (From previous study)

μ_2 = Mean of experimental group (From previous study)

σ = Standard deviation (SD) of control group

Z_α = Z- value (two tail) at a given level of significance e.g. 1.96 at 5% level of significance

Z_β = Z- value (two tail) at a given power e.g. 1.28 at 90% power

PMRT in free breathing technique is expected to give radiation doses to $V_{25\%}$ of heart in 2.5 (SD 2.4) Gy (Rochet, et al., 2014).

PMRT in DIBH technique is expected to give radiation doses to $V_{25\%}$ of heart in 0.1 (SD 0.2) Gy (Rochet, et al., 2014).

Here,

$$\mu_1 = 2.5$$

$$Z_\alpha = 1.96$$

$$\mu_2 = 0.1$$

$$Z_\beta = 1.28$$

$$\sigma = 2.4$$

$$n = \frac{2 \times 2.4^2 \times (1.96 + 1.28)^2}{(2.5 - 0.1)^2} = 23$$

With a 10% allowance for lost to follow up final sample size is $23 + 2.3 = 25$

Selection of Patients

Participants will be selected after fulfilment of inclusion and exclusion criteria.

Inclusion Criteria

1. Histopathologically proven left sided invasive breast cancer patients who underwent modified radical mastectomy.
2. Post mastectomy patients for whom radiotherapy including supraclavicular irradiation is indicated.
3. Patients having ECOG performance status up to 1.

Exclusion Criteria

1. Left sided breast cancer patient underwent BCS.
2. Patient received any chemotherapy other than Doxorubicin, Cyclophosphamide and taxane (Paclitaxel/ Docetaxel) in any settings (neoadjuvant or adjuvant).
3. Patients who have comorbidities that would hinder DIBH (extreme obesity, mental disorder, hypoacusis etc.).
4. Known case of patients with respiratory diseases.
5. Known case of patients with ischemic heart diseases.
6. Patients with previous history of radiotherapy to chest.
7. Male breast cancer patients.

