In BSMMU, data acquired by CT scanner and sentinel will be transferred to central database for automatic tracking of same surface points and breathing pattern with a Catalyst™ system in the treatment room during every fraction, without any manual intervention. IMRT planning will be done by Monaco® Treatment Planning Software (TPS) 5.11 (Elekta AB, Stockholm, Sweden) consist of 6 MV tangential beams.

In other institutes, data will be imported to console automatically from RGSC and RPM™ and a treatment gate window will be established. IMRT planning will be done using TPS Eclipse v15.1 (Varian Medical Systems, Palo Alto, CA, USA) in CMH and v16.1 in Lab aid.

Plans will be evaluated using dose constraint as MSKCC dosimetric planning guidelines for breast IMRT: for heart- $V_{25Gy} < 25\%$, mean dose, $D_{mean} < 20Gy$, maximum dose, $D_{max} \leq 53$ Gy; for lungs- $V_{20Gy} \leq 30\%$, mean dose, $D_{mean} \leq 22$ Gy.

Case Collection

From the OPD of study centres, a total of 50 participants will be recruited after justifying inclusion and exclusion criteria. Before participating in the study, written informed consent will be taken from each selected participant. Interviews will be taken focusing their medical and relevant history by the researcher and will be documented in the preformed data-sheet in respected department with proper privacy. Also, necessary clinical examinations and investigations will be done. Many left sided post mastectomy patients come to these centres regularly for PMRT from all over Bangladesh. Therefore, it will be easy to enrol an adequate number of participants.

Pre-treatment Evaluation

Following procedures will be done to evaluate the participant's condition before treatment:

General examination:

- Complete history, performance status and general physical examination including supraclavicular lymph nodes.

Local examination:

- Right breast examination including draining lymph node areas.
- For left side, chest wall, scar and axilla.

Systemic examination:

- Respiratory system examination.
- Cardiovascular system examination.

Investigations:

- Plain chest radiograph PA view
- ECG
- Echocardiography
- Lung function test

Along with these, all pre surgical imaging and reports will be thoroughly checked.

Intervention

All participants will receive RT with Elekta Versa HD (Elekta AB, Stockholm, Sweden) machine in BSMMU and Varian TrueBeam (Varian Medical Systems, Palo Alto, CA, USA) in other institutes.

Arm A: FB RT arm

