Statistical maximum dose to the critical structure specified measured using predictive dose calculation algorithm integrated in the treatment planning system.

Organ At Risk

Normal tissues which lie adjacent to tumours and may therefore be included within treated volumes, with a risk that the radiation may impair their normal functioning.

Performance Status

Performance status refers to the level of activity to which a patient is capable of.

Respiratory Gating

Respiratory gating refers to the process of limiting the radiation beam to selected portions of the respiratory cycle, thus treating the tumor at a specific position.

Surface Guided Radiotherapy System

Surface imaging systems can help facilitate patient setup and allow for intrafraction monitoring without the use of additional ionizing radiation, this is known as Surface-Guided Radiation Therapy.

V₅

Volume of the structure receiving at least 5 Gy dose expressed as percentage of the total volume of that structure.

V₂₀

Volume of the structure receiving at least 20 Gy dose expressed as percentage of the total volume of that structure.

V₂₅

Volume of the structure receiving at least 25 Gy dose expressed as percentage of the total volume of that structure.

V_{95%}

95% volume of the structure receiving the prescribed dose expressed as percentage of the total volume of that structure.

Analysis of Data

The data will be tabulated in separate tables for both Arm-A and Arm-B. It will be checked, edited, coded manually and finally saved in computer. Data analysis will be done according to the objectives of the study by using the SPSS (Statistical Package for Social Science) software program for Windows, version 21.

Data Presentation

Data will be presented using tables, graphs or charts as appropriate.

Quality Assurance

Quality will be ensured during data collection and analysis.

Timetable of the Study

Ethical Consideration

Ethical issues related to this study will be maintained carefully. In this study, following criteria will be ensured to maintain the ethical standard-

- All participants will be given an explanation of the study including the risks and benefits.
- All participants will be included in the study after taking their informed consent.
- Informed consent form will be supplied in Bengali & English versions.
- It will also be explained to them that they have the right to refuse or accept to participate in the study.

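### The printed sample-size equation gives 21 per arm, not 23, and the heart volume measure that sizes the study is undefined and labelled in Gy; the planned 50 patients are unaffected

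*Protocol*

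**What the plan says.** The Sample Size section (protocol, Materials & Methods) introduces the calculation with "For determination of sample size following formula has been applied" and prints the usual normal-approximation formula for two means, n = 2 × σ² × (Z_alpha + Z_beta)² / (μ1 − μ2)². It sets σ to the control-group SD, Z_alpha to 1.96, and describes Z_beta as "Z- value (two tail) at a given power e.g. 1.28 at 90% power".

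The planning variable is written V25% of heart. Free breathing is expected to give "of heart in 2.5 (SD 2.4) Gy" and breath hold "of heart in 0.1 (SD 0.2) Gy", both attributed to a cited earlier study. The substituted equation ends "1.96 + 1.28)^2}{(2.5 - 0.1)^2} = 23". A 10% allowance for loss to follow-up is then added as 23 + 2.3, and the total is printed as 25. The Grouping section and the dummy tables show that this means 25 per arm and 50 in all.

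Elsewhere, the Operational Definition section defines V25 as "Volume of the structure receiving at least 25 Gy dose expressed as percentage of the total volume of that structure". The planning constraint under Treatment Planning and Evaluation, "for heart- $V_{25Gy} < 25" per cent, uses V25 in the same way. Dummy Table 2 lists heart V25 together with the mean and maximum dose under a column heading that gives the unit as Gy.

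**The concern.** The section shows its formula, every input and the result, so a reader should be able to reproduce the number, and cannot. A sample-size figure that does not follow from its own equation suggests either a slip or an adjustment that was not described. An ethics board or a journal will ask which.

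The unit problem is separate. The quantity that sizes the study carries a symbol with no definition and a unit that does not fit the nearest defined symbol. The same mismatch sits in the template for the cardiac results. Section F of the Data Collection Sheet records V25 of heart with no unit, so nothing downstream would catch the mislabelling before it reached the results table.

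**Working it through.** **Inputs, all from the Sample Size section:** μ1 = 2.5, μ2 = 0.1, σ = 2.4, Z_alpha = 1.96, Z_beta = 1.28. That n is per arm is inferred from 25 per arm and 50 in total.

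**1. The printed equation.** The difference is 2.5 − 0.1 = 2.4, equal to σ, so those terms cancel:

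n = 2 × 2.4² × (1.96 + 1.28)² / 2.4² = 2 × 3.24² = 2 × 10.4976 = 20.995, so 21 per arm.

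The printed 23 is not reproduced; it is 2 per arm higher.

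**2. Could another tabulated Z_beta explain 23?** Keep Z_alpha at the stated 1.96.
- For n to round up to 23, Z_beta must lie above √(22/2) − 1.96 = 1.357 and be at most √(23/2) − 1.96 = 1.431.
- Appendix VIII lists 0.52, 0.84 (0.85), 1.28, 1.64 and 2.33. None is in that range, and neither appendix has any entry between 1.28 and 1.64.
- The protocol calls 1.28 a two-tail value at 90% power. Appendix VII lists 1.28 as the one-tail value at 10% and 1.64 as the two-tail value. Using 1.64 gives 2 × 3.60² = 25.92, again not 23. Appendix VIII confirms 1.28 for 90% power, so the number is right and the description is wrong.

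**3. The allowance.**
- As printed: 23 + 2.3 = 25.3, not 25.
- From the correct result: 21 + 2.1 = 23.1, so 24 per arm. Dividing by 0.9 instead gives 21 / 0.9 = 23.3, also 24.
- Planned: 25 per arm, one more than needed.

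**4. Power at the planned size.** Two-sided 5% two-sample t test, assuming SD 2.4 in both arms (standardised difference 2.4 / 2.4 = 1), from the noncentral t distribution:

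| Per arm | Power |
|---|---|
| 21 | 88.5% |
| 22 | 90.0% |
| 23 | 91.2% |
| 25 | 93.4% |

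A 10% loss from 25 leaves 22.5, that is 22 or 23 per arm, and power of about 90% to 91%.

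**5. The unit.** Only the ratio of the difference to the SD enters the formula, so relabelling 2.5, 0.1 and 2.4 from Gy to per cent leaves n at 20.995. The relevant places compare as follows:

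| Place | Symbol | Unit |
|---|---|---|
| Sample Size | V25% of heart (not defined) | Gy |
| Dummy Table 2 | V25 | Gy, from the column heading |
| Treatment Planning and Evaluation | V25Gy of heart | per cent |
| Operational Definition | V25 | per cent of the structure's volume |

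Table 2 contradicts the definition directly. The Sample Size section uses a symbol that the list of definitions (V5, V20, V25, V95%) does not contain.

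**The case against.** The strongest reply is that none of this affects the trial. An exact two-sample t test at a standardised difference of 1 has 89.97% power at 22 per arm and 91.25% at 23, so 23 is the smallest size reaching 90%, and the abstract says "The data will be analysed using Chi-square test and 't' test". Moreover, the protocol's own SD for breath hold is 0.2. With both SDs the same z-formula needs only (2.4² + 0.2²) × 3.24² / 2.4² = about 10.6 per arm, so 21 against 23 is immaterial.

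Most of this stands, and it is why the point is minor. It does not rescue the text. The section says that the printed formula was applied and presents 23 as its result; it mentions no t-test sizing. A method that happens to give 23 is not evidence that it was used.

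Three stronger readings should be resisted:
- **That the study is too small.** The discrepancy runs the other way: the correct formula result needs fewer patients than planned.
- **That the loss allowance was applied twice.** It is suggestive that 21 plus 10% is 23.1, but the protocol does not say this happened.
- **That the protocol itself shows 2.5 and 0.1 to be percentages.** The likely inference is that V25% means V25, since V25 of heart is the recorded study variable. But the symbol is undefined, and the metric and unit in the cited study cannot be checked from the protocol.

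**Conclusion.** Wrong as written, and minor. The equation gives 20.995, so 21 per arm and not 23, and the allowance sum gives 25.3 and not 25. Both findings are exact arithmetic on printed inputs and rest on no assumption beyond reading n as per arm. The overstatement of 2 per arm is conservative: 24 per arm would meet the stated formula and allowance, and 25 are planned. The power of about 93% at 25 per arm rests on an SD of 2.4 in both arms and no losses.

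The unit conflict between Dummy Table 2 and the definition of V25 is certain. For the Sample Size section, what is certain is an undefined symbol labelled in Gy; which metric the planning values represent remains open. Neither matter changes the 50 patients.

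**What to change.** In the Sample Size section:
- Correct the result of the equation to 21 per arm.
- Restate the allowance as 21 + 2.1 = 23.1, so 24 per arm, and say that 25 per arm (50 in total) is kept and exceeds this.
- Remove the two-tail description from the definition of Z_beta; the value 1.28 stays.
- Check in the cited study which heart metric, and in what unit, the values 2.5 and 0.1 are. Then use one defined symbol and its unit. If they turn out to belong to a measure other than V25, name that measure as the basis of the calculation.

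In Dummy Table 2, give V25 as a percentage of heart volume, in line with the Operational Definition section, and keep Gy for the mean and maximum dose only.

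The cost is one look at the cited source and a few lines of protocol and table wording. Enrolment and study procedures do not change.

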Pulmonary toxicities also occur from RT which may be clinical or sub clinical. Documented ones are- reduced lung function, radiation pneumonitis (RP), lung fibrosis, lung cancer (Lawler et al., 2017). Pre-existing patient-related risk factors for radiation induced lung disease (RILD) are- older age, history of chronic lung disease, smoking, concurrent chemotherapy with RT etc (Marks et al., 2010). No specific threshold is there for RILD, with risks increasing as dose increases (Halperin et al., 2019).

Course of RP is divided into several phases ranging from immediate phase occurring in hours to days to final fibrosis phase occurring in 6–12 months after RT (Gokula et al., 2013) and related with surfactant producing type II pneumocytes. RP risk increases with mean dose to the lung or irradiated lung volume (Oechsner et al., 2019). Incidence of lung cancer \geq 10 years after RT 0.11 ERR per Gy whole lung dose (Taylor et al., 2017).

As patients are becoming long survivors, more patients are at risk of late effects (Duarte et al., 2022). Advanced irradiation techniques are being developed to avoid or reduce these. RT with optimisation of beam angles, DIBH technique, using heart lung shielding Multileaf collimators (MLCs), prone positioning, partial breast irradiation (PBI), IMRT, tomotherapy, proton therapy etc are notable (Taylor et al., 2015). Among these, heart lung shielding MLCs are preferable for upper pole breast cancers and may results in underdose to target volume specially when the PTV is located at lower part; prone positioning is more suitable for sparing lungs but heart dose may vary (Varga et al., 2014) due to variable patients' anatomy and the options for PBI are very selective. Very advanced techniques are also not suitable for resource poor setting due to unavailability.

DIBH is a specialized respiratory gating system. Patients are instructed to hold their breath after a deep inspiration for an extended time. This produces a large enough window to treat the tumor with limited motion (Kepka, 2021). An inflated lung pushes the chest wall up and the heart inferiorly and posteriorly away from the treatment field. This results in substantial exclusion of irradiated heart and lung volumes from the high-dose area without compromising PTV coverage (Stranzl et al., 2008). Ultimately, the heart and left lung receive reduced radiation doses as compared to conventional technique (Yeung et al., 2015).

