The most important issues with DIBH technique are individual patient's anatomical differences (high body mass index- BMI, structural abnormalities, adherence of heart to chest wall) as well as patient's cooperation and reproducibility which often limit the feasibility (Bruzzi et al., 2013). Another important aspect is patient-individualized variables like type of surgery, disease stage (especially nodal involvement affecting field size and shape), RT dose regimen (standard or hypofractionated) etc.

From patient's, DIBH method demands proper understanding of the procedure as well as some degree of effort and cooperation to maintain the breathing pattern during simulation and each treatment session (Borst, et al., 2009). For a complete successful RT session with DIBH, determination of patient benefit and capability, as well as optimal positioning, reproducibility and verification methods, are also required.

The main objective of this study is to evaluate dosimetric benefits of the DIBH RT over FB RT during left sided post mastectomy chest wall irradiation.

Rationale of the Study

Due to high prevalence of breast cancer and various awareness programmes, more patients are being diagnosed and treated now with curative intention.

PMRT plays a vital role in treatment plan and is associated with improved overall survival. As a result, these patients are at long-term risk of cardiac and pulmonary sequels which causes undue morbidity and mortality specially in case of left sided breast cancer. The 2005 Early Breast Cancer Trialists' Collaborative Group (EBCTCG) shows, beneficial effects of PMRT are counterbalanced by a 30% increase in cardiac deaths. So, issue of survivorship is a big concern now.

Various treatment modalities are being developed with these concerns ranging from optimisation of beam angles to utilisation of very advanced methods like tomotherapy or proton therapy. Unique irradiation techniques are also being tailored by simple changes in treatment position or set up. Among all these, DIBH technique utilises the patient's own anatomy by reproducible shift of heart from targeted radiation area due to increased volume of left lung in between.

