8. Bilateral breast cancer patients.
9. Pregnant or lactating women.
10. Age < 18 years.

Criteria of Discontinuation of Treatment

1. Patient's refusal to continue study participation.
2. Justifiable withdrawal at the investigator's discretion.
3. Occurrence of unacceptable issues requiring major modification of treatment.
4. Clear lack of clinical benefit.

Research Instrument

A semi-structured data collection form consisting of sociodemographic information, relevant history, clinical examination and investigations made by the researcher will be used as research instrument (**appendix IV**).

Grouping

Fifty post mastectomy left sided breast cancer patients who meet the inclusion and exclusion criteria will be enrolled in this study. Then they will be divided equally into 2 arms (Arm A and Arm B) by purposive sampling.

Study Procedure

For Arm A participants, CT simulation scans will be performed on a supine breast board by Brilliance, CT Big Bore (Philips, Cleveland, USA) in BSMMU, Biograph mCT Sim edition (Siemens Healthineers AG, Germany) in CMH and Somatom 16 CT (Siemens Healthineers AG, Germany) in other institutes with arms raised above head in supports with free breathing. The board will be angled around 5°-25°, to level participant's chest as horizontal as possible. The head will be extended comfortably with face turned to the right side. Radio-opaque wires will be placed over surgical scars. Skin markers, room laser alignment, and breast-board scale will be used for standard patient positioning. Scans will be acquired with a 4 mm slice width from above the shoulder to include the neck to 5.0 cm below inframammary fold (using right inframammary fold as reference).

For Arm B participants, procedure will be same except the following-

Breath Holding Technique

Participants will be trained for 2-3 days for obtaining the desired breathing cycle by trained technologists. No extra equipment will be needed. At first, they will be assured and asked to relax. Then instructed to breath in and out twice followed by a slow, deep breath in to a comfortable higher level than normal and to hold it for at least 20 seconds then again breath normally. Once they are ready with expected breath holding, simulation will be done.

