During this procedure in BSMMU, SGRT system (C-RAD, Uppsala, Sweden) will be used. At the time of simulation with this system, no marker is usually needed on or around the participant; ceiling mounted laser tracking system in the room automatically monitor for consistency by matching with anterior and lateral tattoos.

In CMH, Varian RGSC (Respiratory Gating for Scanners) and in other institutes, Varian RPM™ system (Varian Medical System, Palo Alto, CA) will be used. A 4-dotted reflective marker box will be placed outside the treatment field between xiphoid level and umbilicus. It will act as an external surrogate to simulate the breathing pattern and tracked by the infrared camera at the foot end of CT couch.

For all patients, audio-visual communication through in-room speakers will assist the participant to follow the optimal breathing pattern. Each participant will have 2 CT simulation scans in this arm. One just like participants in Arm A with FB, used as the reference for treatment setups; and another in DIBH position used for the actual treatment plan.

A 30-35 minute in-room time (which included participant's dressing and undressing, set-up, daily imaging, DIBH practice, and subsequent gated RT delivery) was given to each participant for first RT day. For subsequent days, 15–20-minute time was enough, which is double than the allocated time for radiation delivery with FB.

Contouring

For all participants, contouring will be done as per the Radiation Therapy Oncology Group (RTOG) protocol. For left chest wall, superiorly caudal border of the clavicle head, inferiorly loss of CT apparent right breast tissue, laterally mid axillary line excluding latissimus dorsi muscle, medially sternal–rib junction, posteriorly rib–pleural interface, anteriorly skin will be drawn. Nodal area will be contoured including supraclavicular field. For heart, the superior point is where pulmonary trunk and right pulmonary artery seen separately. The major blood vessels will be excluded but the left anterior descending (LAD) artery will be included in the heart contour as a whole. Lungs and other OARs will be contoured accordingly using the planning system.

Treatment Planning and Evaluation

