Participants will be treated with 40.05 Gy radiation, at 2.67 Gy daily single fraction, 5 days a week, for 3 weeks by IMRT in free breathing technique.

Arm B: DIBH RT arm

Participants will be treated with 40.05 Gy radiation, at 2.67 Gy daily single fraction, 5 days a week, for 3 weeks by IMRT in DIBH technique. As the sentinel (C-RAD, Uppsala, Sweden) and Varian RGSC and RPM™ system (Varian Medical System, Palo Alto, CA) is linked to the corresponding linear accelerator (LINAC), beam-hold will be automatically triggered when participant's breathing falls outside the acceptable range. It will ensure radiation delivery only at deep inspiration.

Variables

Demographic variables:

- Age
- Risk factors
 - Age of menarche
 - Age at first child birth
 - Lactation history
 - Use of oral contraceptive pill

- Age of menopause
- Use of hormone replacement therapy
- Pre-existing hypertension / diabetes mellitus
- Family history breast cancer or ovarian cancer
- Educational status
- Body mass index (BMI)

Clinical variables:

[figure not shown]
- Involved quadrant of the breast
- Histological variety
- Tumor grade
- Hormone receptor and HER-2 receptor status
- Stage of the disease
- Performance status

Study variables:

- Planning target volume
 - Total volume
 - Maximum dose, D_{max}
 - Mean dose, D_{mean}
 - V_{95} of PTV
- Heart
 - Mean heart dose, D_{mean}
 - Maximum heart dose, D_{max}
 - V_{25} of heart
- Left lung
 - Mean dose to left lung, D_{mean}
 - V_{20} of left lung

Data Collection

Findings will be recorded in data collection form (**Appendix-IV**).

Consort Flow Chart

Operational Definition

Deep Inspiration Breath Hold Radiotherapy

The approach of delivering prescribed radiation doses only during breath holding at deep inspiration is considered as deep inspiration breath hold radiotherapy.

Dose Volume Histogram

It is a graphical representation of the dose of radiation received by the critical structures or organs at risk per 2cc volume.

Intensity-modulated radiation therapy

It refers to a radiation therapy technique in which a nonuniform fluence is delivered to the patient from any given position of the treatment beam to optimize the composite dose distribution.

Mean dose

Statistical mean dose to the critical structure specified measured using predictive dose calculation algorithm integrated in the treatment planning system.

Maximum dose

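### Both arms' planning CT stops at a fixed skin landmark and no rule requires the whole left lung to be imaged, so the denominator of left-lung V20 and mean dose is not guaranteed

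*Protocol*

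**What the plan says.** Study Procedure sets the CT range for Arm A: "from above the shoulder to include the neck to 5.0 cm below inframammary fold (using right inframammary fold as reference", in 4 mm slices. For the other arm it says "For Arm B participants, procedure will be same except the following". The exceptions that follow, under Breath Holding Technique, concern training, monitoring equipment and a second scan; none changes the scan length. Each Arm B participant has two scans: a free-breathing one for set-up reference and "another in DIBH position used for the actual treatment plan". Arm B doses are therefore computed on the breath-hold scan.

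Operational Definition gives V20 as "Volume of the structure receiving at least 20 Gy dose expressed as percentage of the total volume of that structure". Variables and Appendix IV, Section F list mean dose and V20 as the left-lung measures, which serve Specific Objective 3. Contouring says of the lungs only "Lungs and other OARs will be contoured accordingly using the planning system". Total volume is recorded for the PTV and for no other structure.

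On what breath hold does to the anatomy, the Introduction says "An inflated lung pushes the chest wall up and the heart inferiorly and posteriorly away from the treatment field", and the Rationale describes a "reproducible shift of heart from targeted radiation area due to increased volume of left lung in between".

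**The concern.** V20 and mean lung dose are whole-organ averages, so they are comparable between patients and arms only if the same organ, complete, is in the denominator. A scan that ends at a set distance below a skin fold fixes a position on the body surface and does not fix how much lung is included. Lung below the last slice cannot be contoured and drops out of the denominator.

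If that lung receives little dose, losing it raises both measures. Breath hold changes the size of the lung, so one surface rule could capture different shares of the organ in the two arms. Left lung is in the title, the research question and Objective 3. With 25 patients per arm, an artefact of a few percentage points in V20 could matter to that comparison.

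**Working it through.** The protocol states no figure on this point, so there is none to reproduce. The check is a sensitivity calculation.

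**Inputs from the protocol**
- The caudal limit is the same in both arms (Study Procedure).
- Arm B is planned on the breath-hold scan (Breath Holding Technique).
- The V20 denominator is the total structure volume (Operational Definition).
- The chest-wall target ends inferiorly where right breast tissue is no longer seen on CT, and the nodal field is supraclavicular (Contouring). Lung more than 5 cm below the fold should therefore be well caudal to the target.

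**Assumptions, because the documents give no values**
- f, the fraction of left lung below the last slice: 0 to 15%.
- Dose d in that lung: 0.5 or 2 Gy, hence no contribution to V20.
- True V20 of 25% or 30% and true mean dose of 12 Gy, as an illustrative scale.

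**Formulas**
- Reported V20 = true V20 / (1−f)
- Reported mean dose = (true mean − f·d) / (1−f)

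**Effect within one arm**

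| f | Factor on V20 | True V20 25% reads | True mean 12 Gy reads (d = 0.5) | (d = 2) |
|---|---|---|---|---|
| 0 | 1.00 | 25.0% | 12.00 Gy | 12.00 Gy |
| 5% | 1.05 | 26.3% | 12.61 Gy | 12.53 Gy |
| 10% | 1.11 | 27.8% | 13.28 Gy | 13.11 Gy |
| 15% | 1.18 | 29.4% | 14.03 Gy | 13.76 Gy |

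**Effect on the comparison**, with an assumed true V20 of 30% in free breathing and 25% in breath hold (true gap 5.0 points)

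| f in Arm A | f in Arm B | Reported A | Reported B | Reported gap |
|---|---|---|---|---|
| 0 | 0 | 30.0% | 25.0% | 5.0 |
| 5% | 5% | 31.6% | 26.3% | 5.3 |
| 0 | 5% | 30.0% | 26.3% | 3.7 |
| 5% | 10% | 31.6% | 27.8% | 3.8 |
| 0 | 10% | 30.0% | 27.8% | 2.2 |
| 0 | 15% | 30.0% | 29.4% | 0.6 |

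**Direction.** The reported ratio B/A is the true ratio times (1−fA)/(1−fB), so on the ratio scale any excess loss in Arm B works against breath hold. In percentage points the excess must be slightly larger. With fA = 5%, the gap stays at 5.0 when 25/(1−fB) = 31.58 − 5 = 26.58, that is, at fB = 5.9%; beyond that it shrinks. Equal loss in both arms enlarges the gap slightly (5/0.95 = 5.3).

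**The case against.** The strongest reply is that no loss of lung is demonstrated. Nothing in the protocol places any lung below a line 5 cm under the fold, and every magnitude above is assumed. That stands.

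A reader might also infer that the loss must be larger in Arm B. The documents do not go that far. The Introduction states downward movement for the heart only. For the lung, the protocol states inflation and greater volume. The reference fold lies on a chest wall that also moves, and the relative movement of fold and lung base is not given. Downward extension of the lung base is a reasonable inference, not a stated fact.

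Other stronger readings fail too:
- **Heart measures.** These would be affected only if part of the heart were cut off, and nothing supports that. The heart V25 figure behind the sample size is not called into question.
- **A problem that could never be noticed.** A cut-off lung would be visible on the planning CT, and the planning system can report organ volume. Section F simply does not collect it.
- **A biased within-patient comparison.** None is planned; the Arm B free-breathing scan is for set-up.

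Contouring follows an RTOG protocol that is not reproduced here and may ask for whole organs. That helps only in part, because a contouring rule does not set scan length and cannot recover lung that was not imaged.

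Finally, a bias against breath hold is conservative. That is fair if the only worry is a false claim of benefit. Objective 3, however, is to measure lung dose under each technique, and an understated benefit is still an error.

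**Conclusion.** The point holds as a gap in a stated rule. The scan limit does not guarantee the denominator of two named left-lung outcomes, in a study whose intervention changes lung volume. If the lung base is cut off, V20 is overstated by a factor of about 1/(1−f), and mean dose by slightly less. If appreciably more is cut off in breath hold than in free breathing, the lung benefit is understated: under the assumed values, a true gap of 5.0 points reads 3.7 with 5% lost in Arm B only and 2.2 with 10%.

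This rests on the missing lung being low dose and on values of f that the documents do not supply. f may be zero in many patients, and a difference between arms is plausible but unproven. It is a cheap improvement of low priority. It has to be made before scanning, because slices not acquired cannot be added later.

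**What to change.** In Study Procedure, for every planning scan in both arms, keep the present caudal limit as a minimum and add that the scan continues until the whole of both lungs is included in the breathing state being scanned. Both lungs are named because Objective 4 also covers right-lung dose.

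In Variables and Appendix IV, Section F, add left-lung total volume, read from the planning system, and a yes/no item stating whether the left lung is complete on the scan. Report the count of incomplete lungs by arm.

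The cost is a few more slices and slightly more imaging dose in some patients, a scan length that must still fit within the breath hold, and two data-sheet fields. It would also give the four centres, with their three CT models, one explicit rule.
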